3.2 STUDY DURATION

Total study duration will be up to 391 weeks (7.5 years):

- The enrollment phase will be up to 156 weeks (3 years).
- The duration of the study for an individual participant may range from approximately 188 to 235 weeks, comprised of a screening phase of approximately 8 weeks, a withdrawal phase of approximately 24 to 45 weeks and a follow-up phase of approximately 156 to 182 weeks.

- The study primary endpoint, measured 52 weeks after the last participant's completion of immunosuppression withdrawal, could be achieved as early as 240 weeks (4.5 years), or as late as 265 weeks (5 years) after enrollment of the first participant.

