3.3.2 Secondary Endpoints

Safety

1. The proportion of participants who develop DSA or de novo anti-HLA antibodies after initiation of immunosuppression withdrawal.
2. The incidence, severity, and timing of acute rejection, steroid resistant rejection, and chronic rejection.
3. The incidence and progression of graft fibrosis in tolerant versus non-tolerant patients.
4. The incidence of graft loss.
5. The incidence of all-cause mortality.
6. The incidence of study-related SAEs.

Effectiveness

1. The proportion of operationally tolerant subjects who remain free of rejection at 3 years after completing immunosuppression withdrawal.
2. Changes in renal function (defined as estimated GFR calculated by CKD-EPI: <http://wwwqxmd.com/calculate-online/nephrology/ckd-epi-egfr>) in tolerant versus non-tolerant participants at 1, 2 and 3 years after completing immunosuppression withdrawal.
3. Changes in Quality of Life in tolerant versus non-tolerant participants and in all participants at baseline versus the end of study participation, as measured by the NIDDK Liver Transplantation Database Quality of Life Form (see Appendix 7).
4. Changes in SF-36 (see Appendix 6) in tolerant versus non-tolerant participants and in all participants at baseline versus the end of study participation.
5. Predictive value and the correlative value of the following parameters with regard to operational tolerance:
 - a. Time post-transplant
 - b. Recipient age

Mechanistic

1. Mechanistic endpoints may assess both the predictive value and the correlative value of the following parameters with regard to operational tolerance:
 - a. Phenotypic or molecular markers of immune senescence and/or exhaustion in T cells recovered from peripheral blood or liver tissue

- b. Donor-specific antibody
- c. Intra-allograft C4d
- d. Recipient anti-donor reactivity in vitro
- e. mRNA transcripts in blood and in liver allograft biopsies
- f. Thymic T cell output
- g. Peripheral blood and tissue miRNA expression
- h. Iron metabolism gene and serum proteins
- i. Microchimerism by STR genotyping
- j. Gut microbiome profile

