6. STUDY PROCEDURES

6.1 VISIT WINDOWS

6.1.1 Scheduled Visits

Appendices 1 through 5-C present the schedule of events for this trial. See Section 6.2 to determine which schedules of visits to follow during the COVID-19 pandemic.

Visit 0 must occur within 56 days of Visit -1. Visit -1 may be done over multiple days following informed consent. The eligibility biopsy should be performed within 10 days of initiating Visit -1.

All other scheduled study visits must occur within the time limits specified below:

- Visit 101: within 7 days of Visit 0.
- Visit 201: Participants who initiate and successfully complete immunosuppression withdrawal should begin post withdrawal follow-up within 2 weeks of the date of completion of the participant's last taper level (see section 3.1.3).
- Visit 301: Participants who initiate but fail to successfully complete immunosuppression withdrawal (see Section 3.1.3.5) should begin safety follow-up within 2 weeks of the date of immunosuppression withdrawal failure.
- Visit RIS6: Participants who successfully complete immunosuppression withdrawal but then restart immunosuppression treatment will complete one additional follow-up visit as outlined in Appendix 4, in addition to post withdrawal follow-up, 26 weeks after immunosuppression is restarted. Appendix 2 visits should continue to occur according the participant's post withdrawal follow-up schedule. For the duration of the COVID-19 pandemic, do not conduct Visit RIS-6.
- Telephone consultations and laboratory evaluations done locally, outside of transplant center study visits, should be completed within:
 - \pm 5 days of the scheduled time points during immunosuppression withdrawal;
 - \pm 5 days of the scheduled time points within the first 26 weeks after completing immunosuppression withdrawal;
 - \pm 7 days of the scheduled time points during follow-up weeks 26-52;
 - \pm 14 days of the scheduled time points after 52 follow-up weeks.
- Up to 3 nonconsecutive pauses (up to 4 weeks each) may occur during Visits 101-111 (if needed) as outlined in section 3.1.3.4.
- All non-biopsy visits to the transplant center throughout the study should be completed within \pm 2 weeks of the scheduled time points listed in Appendices 1 through 5-C. Biopsy Visits 204 and 208 should be completed within \pm 4 weeks of the scheduled time points listed in Appendix 2. For

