6.8 MANAGEMENT OF ACUTE REJECTION

Immunosuppression will be reinstated for all participants who experience biopsy-confirmed rejection or presumed rejection. Investigators may treat rejection according to institutional standard. The following however are recommended guidelines based on previous experience in liver allograft immunosuppression withdrawal trials:

- Allograft dysfunction with *no acute rejection or indeterminate for acute rejection*, and without other explanatory diagnosis should be treated at the discretion of the site investigator with reinstitution of the baseline IS (regimen employed before initiation of IS withdrawal). If liver tests do not improve within 4 weeks, repeat biopsy should be considered prior to further escalation of treatment.
- *Mild acute rejection* should be treated initially with reinstitution of baseline IS. If liver tests do not improve within 2 weeks, dose increase or addition of 20 mg oral prednisolone (or equivalent) should be considered. Corticosteroids will be rapidly tapered down over a 4 week period. A second biopsy can be performed at any time at the investigator's discretion.

- *Moderate acute rejection without jaundice and with mild biochemical abnormalities* should be treated with reinstitution of baseline IS and 20 mg oral prednisolone (or equivalent) with rapid taper down of steroid doses over a 4 week period. If liver tests do not improve within 2 weeks, conversion or addition of another agent should be considered prior to corticosteroids. A second biopsy can be performed at any time at the investigator's discretion.
- *Moderate acute rejection with marked biochemical abnormalities and/or jaundice, severe acute rejection, or chronic rejection*, should be treated according to site standard of care. Antibody treatment should be reserved for steroid-resistant acute rejection proven by repeat liver biopsy.

Participants who experience biopsy-confirmed rejection or presumed rejection prior to completing immunosuppression withdrawal will undergo safety follow-up per Appendix 3. If the episode of biopsy-confirmed rejection or presumed rejection occurs after the completion of immunosuppression withdrawal, the participant will continue on post withdrawal follow-up per Appendix 2. If the participant is restarted on immunosuppression therapy, the subject will be followed concurrently on Appendix 4 (except during the duration of the COVID-19 pandemic).

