APPENDIX 2. SCHEDULE OF EVENTS – POST WITHDRAWAL FOLLOW-UP

IMPORTANT NOTE: For the duration of the COVID-19 pandemic, follow the COVID-19 Modified Appendix 2-C instead (per Section 6.2).

IS Withdrawal Follow-up Weeks ¹	0	13	26	52	78	104	130	156
Visit Number ^{2,3}	201 ⁴	202	203	204	205	206	207	208
General Assessments								
Limited physical exam	X	X	X	X	X	X	X	X
Vital signs including weight	X	X	X	X	X	X	X	X
Quality of Life Questionnaires	X		X	X	X	X	X	X
Status Change since prior visit ⁵	X	X	X	X	X	X	X	X
Telephone consultation ⁶	X							X
ECG					Prior to restarting tacrolimus ⁷			
Local Clinical Laboratory Assessments								
LFTs ⁸		Every 4 weeks		Every 8 weeks			Every 12 weeks	
CBC w/differential	X	X	X	X	X	X	X	X
Comprehensive metabolic panel, includes LFTs	X	X	X	X	X	X	X	X
Liver biopsy				X				X
Mechanistic Laboratory Assessments								
Frozen PBMC collection	X		X	X		X		X
Serum collection	X		X	X		X		X
Whole blood collection	X		X	X		X		X
Urine pellet collection	X		X	X		X		X
Fecal collection ⁹	X		X	X		X		X
Liver biopsy collection				X				X

¹ The assessments outlined in Appendix 2 should be completed for all participants who initiated and successfully completed immunosuppression withdrawal. Follow-up should begin within 2 weeks of the date of completion of the participant's last taper level (see section 3.1.3).

² If a for-cause liver biopsy is needed, follow all assessments specified in Appendix 5. If the for-cause biopsy occurs within 8 weeks prior to a scheduled protocol visit, complete all clinical and mechanistic assessments listed in Appendix 5 at the time of the for-cause biopsy. The for-cause biopsy visit will take the place of the scheduled protocol visit.

³ If a participant restarts immunosuppression after successfully completing immunosuppression withdrawal, follow the assessments listed in Appendix 4. **Appendix 2 visits to be completed in addition and concurrently with Appendix 4.**

⁴ For any participant requesting early termination from the study, follow all assessments specified here, Visit 201.

⁵ Includes assessment of change in adverse events and concomitant medications. Changes should be recorded in eCRFs as appropriate.

⁶ Complete following the performance of each liver function test assessment done outside of a transplant center clinical visit; AEs and concomitant medications to be reviewed.

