APPENDIX 3. SCHEDULE OF EVENTS – SAFETY FOLLOW-UP

IMPORTANT NOTE: For the duration of the COVID-19 pandemic, follow the COVID-19 Modified Appendix 3-C instead.

Safety Follow-up Weeks ¹	0	13	26	52	104	156
Visit Number ²	301 ^{3,4}	302	303	304	305	306
General Assessments						
Limited Physical Exam	X	X	X	X	X	X
Vital signed including weight	X	X	X	X	X	X
Quality of Life Questionnaires	X		X	X	X	X
Status Change since prior visit ⁵	X	X	X	X	X	X
Telephone consultation ⁶	X					X
ECG			Prior to restarting tacrolimus if on MMF monotherapy ⁷			
Local Clinical Laboratory Assessments						
LFTs ⁸		Every 4 weeks		Every 8 weeks		Every 12 weeks
CBC w/differential	X	X	X	X	X	X
Comprehensive metabolic panel, includes LFTs	X	X	X	X	X	X
Mechanistic Laboratory Assessments						
Frozen PBMC collection	X		X	X	X	X
Serum collection	X		X	X	X	X
Whole blood collection	X		X	X	X	X
Urine pellet collection	X		X	X	X	X
Fecal collection	X		X	X	X	X

¹ The assessments outlined in Appendix 3 should be completed for all participants who initiated but did not complete immunosuppression withdrawal. Follow-up should begin within 2 weeks of the date of immunosuppression withdrawal failure (see section 3.1.3.5).

² If a for-cause liver biopsy is needed, follow all assessments specified in Appendix 5. If the for-cause biopsy occurs within 8 weeks prior to a scheduled protocol visit, complete all clinical and mechanistic assessments listed in Appendix 5 at the time of the for-cause biopsy. The for-cause biopsy visit will take the place of the scheduled protocol visit.

³ If a for-cause liver biopsy visit took place within 8 weeks of visit 301, all mechanistic assessments listed in Appendix 5 at the time of the for-cause biopsy visit should be completed in lieu of mechanistic assessments listed for visit 301.

⁴ For any participant requesting early termination from the study, follow all assessments specified here, Visit 301.

⁵ Includes assessment of change in adverse events and concomitant medications. Changes should be recorded in eCRFs as appropriate.

⁶ Complete following the performance of each liver function test assessment done outside of a transplant center clinical visit; AEs and concomitant medications to be reviewed.

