Changes in renal function (defined as estimated GFR calculated by CKD-EPI) in tolerant versus non-tolerant participants at 1, 2 and 3 years after completing immunosuppression withdrawal for tolerant subjects and failure of withdrawal for non-tolerant subjects.	
Baseline eGFR will be calculated from data collected at Visit 0. If Visit 0 data is missing, Visit -1 data will be used. Data collected closest to 1-year post completion/failure, within +/- 2 months, will be used to calculate eGFR at 1. The same process will be followed for 2 and 3-years after completion/failure.
 
eGFR will be calculated using the CKD-EPI equation:
 $\text{GFR} = 141 * \min(\text{Scr}/\kappa, 1)^\alpha * \max(\text{Scr}/\kappa, 1)^{-1.209} * 0.993^{\text{Age}} * 1.018 \text{ [if female]} * 1.159 \text{ [if black]}$ 
Scr: serum creatinine (mg/dL) κ: 0.7 for females and 0.9 for males α: -0.329 for females and -0.411 for males
 
Change in eGFR will be calculated as: 1-year post completion/failure eGFR – baseline eGFR
 
Thus positive value will indicate increase kidney function.
 
Changes will be summarized descriptively by tolerance status.
	ITT, PP
Changes in Quality of Life in tolerant versus non-tolerant participants and in all participants at baseline versus the end of study participation, as measured by the NIDDK Liver Transplantation Database Quality of Life Form.	The questionnaire filled out at Visit 0 will serve as the baseline questionnaire. The questionnaire filled out closest to the end of study participation will serve as the end of study questionnaire. For subjects	ITT, PP

	
with complete follow-up, this will be the questionnaire completed at Visit 208 or Visit 306.
 
The questionnaire will be summarized into five domains as outlined by Bell et al. The domains include measures of disease, psychological status, personal function, social and role function, and general health perception.
 
The change in each domain will be calculated as: Domain Score at End of Study – Domain score at Baseline.
 
The baseline, end of study, and change from baseline domain scores will be summarized descriptively by tolerance status.
 
If the data permits, a spaghetti plot visualizing each component score over time will be produced. Each graph will have two panels—one depicting the tolerant subjects, the other depicting the non-tolerant subjects.
	

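### The SAP times eGFR years 1–3 from failure for all non-tolerant participants, but those who complete withdrawal and fail later are seen on a schedule timed from completion, so failure after about week 9 leaves no scheduled year-3 value on nominal dates

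*SAP*

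**What the plan says.** Protocol 3.3.2 defines the renal endpoint as change in eGFR "in tolerant versus non-tolerant participants at 1, 2 and 3 years after completing immunosuppression withdrawal". SAP Table 7-2 (Section 7.3) repeats this and then adds a split origin: completion "for tolerant subjects and failure of withdrawal for non-tolerant subjects". The method cell reads "Data collected closest to 1-year post completion/failure, within +/- 2 months, will be used to calculate eGFR at 1", with the same process for years 2 and 3.

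The protocol runs two follow-up schedules:

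- Appendix 2: "The assessments outlined in Appendix 2 should be completed for all participants who initiated and successfully completed immunosuppression withdrawal". It is timed from completion.
- Appendix 3: "The assessments outlined in Appendix 3 should be completed for all participants who initiated but did not complete immunosuppression withdrawal". It is timed from failure.

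For rejection after completion, Protocol 6.8 says "the participant will continue on post withdrawal follow-up per Appendix 2". Protocol 3.2 gives "a follow-up phase of approximately 156 to 182 weeks". On visit windows, Protocol 6.1.1 says "Biopsy Visits 204 and 208 should be completed within" 4 weeks either side of the scheduled date, other transplant-center visits within 2 weeks, and Visit 208 up to 6 months late during the pandemic.

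Under SAP 7.2.1, anyone who does not meet the tolerance definition is non-tolerant, including a participant with no week-52 biopsy. SAP Section 11, for changes from the protocol, shows no entry in the text available.

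**The concern.** The SAP origin depends on tolerance status, while the visit schedule depends on whether withdrawal was completed. The two agree for tolerant participants and for those who never complete. They disagree for participants who complete, enter Appendix 2, and then become non-tolerant through rejection or an unfavorable week-52 biopsy. Their eGFR targets move later by the time from completion to failure, but their visits do not move.

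Renal function is part of secondary objective 3 (Protocol 2.2), and the SAP mock tables have a Year 3 row. SAP Section 3 imputes nothing unless stated. If the rule is followed as written, the year-3 non-tolerant column would come largely from participants who never completed. Visit 208 would meanwhile go unused as the year-3 value for the others, although it gives a creatinine at the protocol's own three-year point.

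**Working it through.** **Inputs**

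- Window: 2 months = 60.875 days / 7 = 8.7 weeks (8.0 to 8.9 depending on how months are counted).
- Appendix 2 metabolic panels: weeks 0, 13, 26, 52, 78, 104, 130 and 156 after completion. Interim liver-test draws are direct bilirubin, ALT and GGT, so they give no creatinine.
- Appendix 3 panels: weeks 0, 13, 26, 52, 104 and 156 after failure.
- Failure week *f*, counted from completion, from 0 to 52. Assumption: the failure date is the date of the rejection or of the failing biopsy.

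**The plan's own duration.** Screening + withdrawal + follow-up: 8 + 24 + 156 = 188 weeks and 8 + 45 + 182 = 235 weeks. Both match Protocol 3.2, so 182 weeks is the longest follow-up intended.

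**Appendix 3 participants.** Years 1, 2 and 3 from failure are weeks 52, 104 and 156, each with a scheduled panel. The failure origin works for them.

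**Year 3 for completers who fail.** The target is week *f* + 156. The last panel qualifies if *f* + 156 − 8.7 ≤ week of Visit 208, so *f* ≤ week of Visit 208 − 147.3.

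| Visit 208 held at (weeks after completion) | Latest *f* with a year-3 panel |
|---|---|
| 156, nominal | 8.7 |
| 160, at +4 weeks | 12.7 |
| 162, as above with Visit 201 held 2 weeks after completion | 14.7 |
| 182, pandemic +6 months (about 26 weeks) | 34.7 |
| 184, pandemic with the same Visit 201 lag | 36.7 |

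For a week-52 biopsy failure the target is 52 + 156 = 208, and 208 − 182 = 26 weeks beyond the stated maximum (208 − 184 = 24 with the Visit 201 lag). SAP 7.2.1 accepts an endpoint biopsy from week 44: 44 + 156 = 200, and 200 − 182 = 18. All exceed 8.7.

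**Years 1 and 2, nominal dates.** From week 52 the panels are 26 weeks apart, and two windows of 8.7 weeks do not span 26. For year 1 (target *f* + 52) the panels at weeks 52, 78 and 104 cover *f* = 0–8.7, 17.3–34.7 and 43.3–52. Year 2 gives the same ranges from weeks 104, 130 and 156. Failures at about weeks 9–17 and 35–43 therefore have no nominal panel in either year. With visit windows and the Visit 201 lag used in the best direction, the ranges with no panel in any of the three years shrink to 14.7–15.3 and 38.7–39.3.

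**Extra panels.** Appendix 4 adds one panel 26 weeks after restart. The year-1 window is 43.3–60.7 weeks after failure, so this panel helps only if restart follows failure by 17.3 to 34.7 weeks. If restart is by week 52, the panel falls at week 78 or earlier, too early for year 3. Post-rejection visits (Appendix 5) include a panel every 13 weeks, but only until liver tests normalize.

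**Missing biopsy.** The Study Definitions list what counts as failed withdrawal: rejection or presumed rejection, taking more than 45 weeks, and Table 1 findings at week 52. A missing biopsy fails the primary endpoint (Protocol 9.2.1; SAP 7.2.1) but is not on that list, so no date exists from which to count.

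**The case against.** The best defense is that the method cell's completion/failure wording means completion for anyone who completed and failure for anyone who did not. The protocol uses a failure date to start a visit schedule only for Visit 301, and the neighboring quality-of-life rows pair Visit 208 with Visit 306. That may well be the intent. It does not settle the matter, because the endpoint cell assigns the origin explicitly by tolerance status. A programmer following it would use failure.

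A second defense is that SAP 7.1.2 admits all data regardless of timing. That gives way where a window is stated, as here. Event-driven panels may fill some gaps, but none is scheduled for year 3.

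A third is that time since failure is a legitimate choice, and that the protocol's origin is undefined for participants who never complete, so the SAP had to adapt it. This stands: an adaptation was needed, but only for those participants.

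A reader might also infer that whole ranges of failure dates yield no eGFR in any year. That holds on nominal dates only; permitted visit windows largely close the gaps at years 1 and 2. Nor is Visit 208 always unused: for failures at about weeks 43–52 it becomes the year-2 value.

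**Conclusion.** The point holds for one subgroup: participants who successfully complete withdrawal and become non-tolerant by week 52. On nominal dates they have no scheduled year-3 eGFR once failure is later than about week 9. The limit is about weeks 13–15 with regular visit windows and about weeks 35–37 with the pandemic window. Failures near week 52 are out of reach under every permitted window. Completers who lack only the week-52 biopsy cannot be dated at all under the rule.

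The documents do not give the timing or number of such failures. Protocol 1.3.1 shows that the group need not be empty: in the non-viral arm of an earlier trial, 4 of 9 who completed withdrawal later resumed immunosuppression for rejection. It does not say when, so it cannot size the loss here.

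A reader might infer that the year-3 comparison fails for non-tolerant participants generally, or that the trial's main result is affected. The documents support neither. Appendix 3 participants are fully covered, the endpoint is secondary and summarized descriptively, and no primary result or power figure depends on it. The reported n would show the shortfall but not repair it. This should be corrected before analysis.

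**What to change.** In SAP Table 7-2:

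1. Use the completion date for every participant who successfully completes withdrawal within 45 weeks and enters Appendix 2, whatever their later tolerance status and whether or not the week-52 biopsy was done. Visits 204, 206 and 208 then supply years 1, 2 and 3. The largest regular deviation is 4 weeks, or 6 with a 2-week Visit 201 lag, both inside 8.7.
2. Keep the failure date for participants followed on Appendix 3, including those who exceed 45 weeks, and record this departure from the protocol origin in SAP Section 11.
3. State whether a pandemic-delayed Visit 208 outside 2 months counts as year 3. It can be about 26 weeks late, for tolerant and non-tolerant completers alike.
4. State the small downside. For completers who fail late, year 1 reflects time since completion, partly or wholly off immunosuppression, rather than time since failure.

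The cost is SAP wording and slightly more programming. No new data are needed.

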the duration of the COVID-19 pandemic, Biopsy Visit 208 should be completed -4 weeks to +6 months of the scheduled time point listed in Appendix 2-C.

- If a participant needs a for-cause biopsy within 8 weeks prior to a scheduled protocol visit, complete all clinical and mechanistic assessments listed in Appendix 5 at the time of the for-cause biopsy.
 - If the scheduled protocol visit occurs during Appendix 1A, complete all clinical assessments noted for the Appendix 1A visit but do not complete any mechanistic collections.
 - If the scheduled protocol visit is listed in Appendices 2-4, the for-cause biopsy visit will take the place of the scheduled protocol visit.
- If the Appendix 4 visit occurs within 1 month (4 weeks) of a scheduled protocol Appendix 2 visit, complete the Appendix 2 visit while collecting all mechanistic samples listed in the Appendix 4 visit in lieu of completing an additional visit.

Table 4. Frequency of Liver Function Tests

Population	Timing	Frequency
For all participants who initiate immunosuppression withdrawal	During immunosuppression withdrawal	Every 3 weeks*
	≤ 26 weeks post immunosuppression withdrawal	Every 4 weeks
	26-52 weeks post immunosuppression withdrawal	Every 8 weeks
	> 52 weeks post immunosuppression withdrawal	Every 12 weeks
	During Rejection	Liver function tests after the rejection episode per standard of care until resolution as determined by the investigator
Additional assessment for participants who successfully complete immunosuppression withdrawal and then restart immunosuppression therapy	26 weeks post immunosuppression restart	Once

*Every 2 weeks between Visits 103-105.

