6.4 CLINICAL LABORATORY ASSESSMENTS

6.4.1 Recipient

These laboratory assessments may be performed at study sites or at local laboratories:

- Hematology – CBC with differential and platelets
- Comprehensive Metabolic Panel (Na, K, Cl, HCO₃, BUN, creatinine, glucose, albumin, total bilirubin, direct bilirubin, GGT, AST, ALT, alkaline phosphatase)
- Urine or blood pregnancy test

- Liver Function Tests (Direct bilirubin, ALT, GGT)
- Autoantibody panel (ANA, AMA, SMA, LKM, quantitative IgG)
- CMV (IgG) and EBV (IgG and IgM) serologies
- HIV-1/2 antigen-antibody immunoassay
- Hepatitis C antibody test
- HBV surface antigen and HBV DNA PCR
- Estimated GFR as determined by calculated CKD-EPI
- CNI levels
- Liver biopsy
 - Participants who are screen failures (see Section 3.1.1) may be rescreened. If a rescreened participant completed a protocol biopsy that met eligibility (see Section 4) during their initial screening window (6.1.1), an investigator may request that the candidate's data is reviewed by a committee consisting of the NIAID Medical Monitor, the ITN Clinical Trial Physician and the Protocol Chair. This committee will adjudicate whether the participant may use the biopsy previously completed in place of a new screening biopsy.

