APPENDIX 2-C. (COVID-19 MODIFIED) SCHEDULE OF EVENTS – POST WITHDRAWAL FOLLOW-UP

IS Withdrawal Follow-up Weeks ¹	0	13	26	52	78	104	130	156
Visit Number ²	201 ³	202	203	204	205	206	207	208
General Assessments								
Limited physical exam								X
Vital signs including weight								X
Quality of Life Questionnaires ⁴				X	X	X	X	X
Status Change since prior visit								X
Telephone consultation ⁵	X							X
ECG				Prior to restarting tacrolimus ⁶				
Local Clinical Laboratory Assessments								
LFTs ⁷				Every 8 weeks		Every 12 weeks		
CBC w/differential			X	X	X	X	X	X
Comprehensive metabolic panel, includes LFTs			X	X	X	X	X	X
Liver biopsy								X
Mechanistic Laboratory Assessments								
Frozen PBMC collection								X
Serum collection								X
Whole blood collection								X
Urine pellet collection								X
Fecal collection								X
Liver biopsy collection								X

¹ The assessments outlined in Appendix 2 should be completed for all participants who initiated and successfully completed immunosuppression withdrawal. Follow-up should begin within 2 weeks of the date of completion of the participant's last taper level (see section 3.1.3).

² If a for-cause liver biopsy is needed, follow Appendix 5.

³ For any participant requesting early termination from the study, collect the following assessments if possible: telephone consultation with AE and concomitant medication update, CBC with diff, and comprehensive metabolic panel including LFTs.

⁴ Complete Quality of Life assessment by mail.

⁵ Complete following the performance of each liver function test assessment done outside of a transplant center clinical visit; AEs and concomitant medications to be reviewed.

⁶ For participants who need to restart tacrolimus for biopsy-confirmed or presumed acute rejection (see section 6.8). A follow-up ECG will be performed within 7 days after tacrolimus has been restarted. ECG findings will be monitored per the site's standard of care until the participant is taking a stable dose of tacrolimus. Evidence of a prolonged QTc interval will be appropriately evaluated and treated.

⁷ If participant experiences a rejection episode, complete liver function tests per standard of care until resolution as determined by the investigator. Record all liver function tests performed during a rejection episode in EDC.

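### Under the pandemic-only window, a compliant Visit 208 can fall outside the SAP's ±2-month limit and leave a tolerant participant with no scheduled year-3 eGFR

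*SAP*

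**What the plan says.** **Analysis window.** For change in renal function, SAP Table 7-2 (section 7.3) states for year 1: "Data collected closest to 1-year post completion/failure, within +/- 2 months, will be used to calculate eGFR at 1". It then adds: "The same process will be followed for 2 and 3-years after completion/failure". Years are counted from completion of withdrawal for tolerant participants and from "failure of withdrawal for non-tolerant subjects". SAP section 7.1.2 uses all data whatever their timing unless a limit is stated, and here one is. SAP section 3 rules out imputation unless it is specified, and none is specified for eGFR.

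**Visit window.** Protocol section 6.1.1 gives the routine rule: "Biopsy Visits 204 and 208 should be completed within" 4 weeks either side of the scheduled time. For the duration of the pandemic it substitutes: "Biopsy Visit 208 should be completed -4 weeks to +6 months of the scheduled time point listed in Appendix 2-C".

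**Where creatinine comes from.** Protocol section 6.4.1 lists it in the metabolic panel ("BUN, creatinine, glucose, albumin, total bilirubin, direct bilirubin, GGT, AST, ALT, alkaline phosphatase") but not in the separate liver tests: "Liver Function Tests (Direct bilirubin, ALT, GGT". In Appendix 2-C the row "Comprehensive metabolic panel, includes LFTs" is marked at weeks 26, 52, 78, 104, 130 and 156. The 12-weekly draws after week 52 are liver tests only.

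**The concern.** The two windows were evidently set independently. The ±2 months in the SAP comfortably covers the routine visit window but not the pandemic one. A site can follow the protocol exactly and still produce a week-156 creatinine that the SAP will not accept.

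Other data from a late Visit 208 are kept. In Table 7-2, fibrosis change uses the last available biopsy, and both quality-of-life instruments use the questionnaire nearest the end of participation. Under SAP section 7.2.1, even a late primary-endpoint biopsy is used. The creatinine drawn at the same visit is the exception.

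Year-3 eGFR by tolerance status is a named secondary effectiveness endpoint. Protocol section 1.4 gives preservation of renal function as a benefit of stopping the calcineurin inhibitor, and year 3 is the longest-term look at it. The participants followed on Appendix 2-C include every tolerant one, so the missing values would not be a random subset.

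**Working it through.** The plan gives no sample size, power or expected loss for eGFR, so there is no stated figure to reproduce for this endpoint. The 24/36 split used in step 6 comes from protocol section 9.3 (40% of 60). The exact interval quoted there reproduces: 24/60 gives 27.56% to 53.46%, against the stated 27.6% to 53.5%.

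Conventions: 1 month = 365.25/12/7 = 4.348 weeks; year 3 = week 156; follow-up week 0 is taken as the completion date.

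1. **SAP year-3 window, tolerant participant.** 2 × 4.348 = 8.7 weeks, so 156 - 8.7 = 147.3 to 156 + 8.7 = 164.7.

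2. **Visit 208.**
   - Routine: weeks 152 to 160, wholly inside step 1, so no loss.
   - Pandemic: week 152 to 156 + 6 × 4.348 = 182.1.
   - Permitted late time beyond the SAP window: 26 - 8.7 = 17.3 of 26 weeks (67%). As a share of the whole permitted range: (182.1 - 164.7)/(182.1 - 152) = 17.4/30.1 = 58%. These are shares of calendar time, not of participants.

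3. **Scheduled substitute.** Visit 207 is at week 130, or week 132 at the end of a ±2-week window. 147.3 - 132 = 15.3 weeks too early. No other scheduled panel lies between Visits 207 and 208. Appendix 5-C draws a panel at a for-cause biopsy, but only if one is needed.

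4. **Appendix 3 participants.** Visit 306 has no biopsy and no extension. At ±2 weeks it falls in weeks 154 to 158, inside the window when counted from the start of safety follow-up.

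5. **Non-tolerant participants who completed withdrawal and failed f weeks later.** Under protocol section 6.8, those who reject after completion stay on the Appendix 2 schedule, so they share the Visit 208 window. Their year-3 window is f + 147.3 to f + 164.7.
   - f = 13: it opens at week 160.3, after the routine Visit 208 range (ends week 160).
   - f of about 17.4 or more: it closes at week 182.1 or later, so a late Visit 208 can no longer overshoot it.
   - f = 35: it opens at week 182.3, after the latest permitted Visit 208.
   - f = 52: weeks 199.3 to 216.7, beyond the 182-week maximum follow-up in protocol section 3.2.

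   A failure at 13 weeks or more therefore loses its year-3 value even when Visit 208 is on time.

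6. **Illustration only (24 tolerant, 36 non-tolerant).** Let s be the share of tolerant participants with Visit 208 more than 8.7 weeks late and no other creatinine in the window. Tolerant values lost = 24s: 6 at s = 0.25, 12 at s = 0.5, 24 at s = 1. Let L be the number who failed after completion. I take L = 3 as a low value. For a high value I use the 4 of 9 completers who resumed immunosuppression in the earlier trial (protocol section 1.3.1): completers = 24/(5/9) = 43.2, so L is about 19.
   - s = 0.5, L = 3: tolerant loss 12/24 = 50%; non-tolerant at most 3/36 = 8%.
   - s = 0.25, L = 19, all failing at 35 weeks or later: tolerant loss 6/24 = 25%; non-tolerant 19/36 = 53%.

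   The overall direction reverses within the plausible range.

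**The case against.** The best defence is that the extension postpones a biopsy, not a blood test. Appendix 2-C lists the metabolic panel among local laboratory assessments and marks it at six time points, while the examination, vital signs and biopsy are marked only at week 156. Section 6.4.1 allows local laboratories, and section 6.1.1 gives local draws ±14 days after week 52. On that reading an on-time week-156 creatinine is already permitted. The SAP's closest-value rule would also accept an unscheduled one. This stands as far as it goes: a local draw would rescue the value. But nothing requires a separate draw when Visit 208 is postponed, so the outcome depends on local practice.

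A second defence is that keeping a 3.5-year value out of a 3-year estimate is a legitimate choice, and that a wider window for Appendix 2-C alone would create a timing imbalance. That is fair, and it is why any wider window should apply to both groups and prefer on-time values.

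Third, this is one of three time points of a secondary endpoint that the SAP summarises descriptively; the Visit 208 extension does not touch years 1 and 2. That limits the weight of the point but does not remove the conflict.

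A reader might infer that compliant values are being discarded, that the loss falls on the tolerant side only, or that it is selective by site. The documents support none of these. They report no delays, overall or by site. Participants who fail after completion share the Visit 208 window and have a further loss of their own through the failure-date anchor.

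**Conclusion.** The conflict between the two windows is real and needs no outside data to establish. Under the pandemic rule, a compliant Visit 208 more than about 8.7 weeks late (about 17 of the 26 permitted late weeks) can leave a tolerant participant with no scheduled year-3 eGFR. Routine timing causes no loss.

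An actual loss requires both a delay of that length and no local or unscheduled creatinine between about weeks 147.3 and 164.7. How often that happens cannot be determined from the documents. Tolerant participants are at greater risk from this mechanism than Appendix 3 participants, but the net direction of all year-3 missingness is unknown. The point merits a correction before analysis; it does not affect the primary endpoint.

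**What to change.** 1. **Protocol section 6.1.1 and Appendix 2-C.** State that when the Visit 208 biopsy is postponed, the week-156 metabolic panel is still drawn on schedule, locally if needed, within the existing ±14 days. This helps only participants who have not yet passed that point.

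2. **SAP Table 7-2, year 3.** Use the creatinine closest to the anniversary within -2 to +6 months, with the same rule for tolerant and non-tolerant participants so that on-time values take precedence. Report actual time since completion or failure, and year-3 missingness by tolerance status. Give the ±2-month analysis as a sensitivity analysis.

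The cost is a wording change in each document and the draw of a panel that is already scheduled. The downside is that some year-3 values will be up to 6 months late; reporting actual times and the sensitivity analysis discloses this. The wider window does not recover values from participants who failed long after completion (at f = 52 it still opens at week 199.3), which is why missingness by group should be shown.
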